8.2.2 Serious Adverse Events

Serious Adverse Event (SAE): defined as any AE that (at any dose):

- Results in death

- Is life-threatening. NOTE: The term "life-threatening" refers to an event in which the subject was at risk of death at the time of the event; it does not refer to an event which hypothetically might have caused death if it were more intense
- Requires inpatient hospitalization or prolongs existing hospitalization
- Results in persistent or significant disability/incapacity
- Is a congenital anomaly/birth defect
- May jeopardize the subject or may require intervention to prevent one of the outcomes listed above. Medical and scientific judgment should be exercised in deciding if these events should be considered serious. Examples of such events are intensive treatment in an emergency room or at home for allergic bronchospasm, blood dyscrasias or convulsions that do not result in hospitalization, or development of drug dependency or drug abuse

In addition, an AE that results in overdose or produces congenital abnormality or cancer is always considered an SAE.

A subject admitted to a hospital as a result of an AE, even if released on the same day, would qualify for inpatient hospitalization. An emergency room visit that results in admission to the hospital would also qualify for inpatient hospitalization. However, emergency room visits that do not result in admission to the hospital would not qualify for inpatient hospitalization and, instead, should be evaluated for one of the other criteria for SAEs (e.g., life-threatening AE or medically significant event).

Hospitalization scheduled before a subject enrolls in the study is not the result of a treatment-emergent AE, and therefore events leading to such hospitalization will not be considered study AEs or SAEs. During the study, if a subject has elective surgery for a condition present at inclusion into the study, and the condition did not worsen during the study, the reason for elective surgery (and resulting hospitalization, if applicable) should not be considered or reported as an SAE. (Surgery or hospitalization should always be reported as an outcome of an AE.) For AEs that result in persistent or significant disability/incapacity, disability/incapacity refers to a substantial disruption of a subject's ability to carry out normal life functions.

The investigator must also submit documentation of the following to the Institutional Review Board, Ethics Committee, or Research Ethics Board (collectively referred to as an IRB):

- Center-specific SAEs and follow-up: The type of serious event that must be submitted (e.g., all or only suspected), as well as the required timing of submission (e.g., within 10 days of occurrence), is defined by the IRB and regulations/guidance from regulatory authorities.
- Any documentation provided by the Sponsor regarding reportable SAEs from the study: The Sponsor will provide documentation of reportable events to the investigator, as specified in [Section 8.7](#).

The investigator should ensure that the subject receives appropriate medical treatment and that the subject is followed up until the SAE resolves or becomes chronic, as defined in [Section 8.4](#).

8.3 Adverse Event Descriptions

8.3.1 Intensity

The intensity of AEs will be characterized as mild, moderate, or severe, as follows:

- **Mild:** Usually transient, requiring no special treatment, and does not interfere with the subject's daily activities
- **Moderate:** Introduces a low level of inconvenience or concern to the subject and may interfere with daily activities, but is usually ameliorated by simple therapeutic measures
- **Severe:** Significantly interferes with a subject's usual daily activities and requires systemic drug therapy or other treatment, if available

8.3.2 Relationship to Study Treatment

The causal relationship to study drug or treatment will be determined by the investigator according to best medical judgment, as follows:

- **Suspected:** There is a reasonable possibility that the AE is associated with use of the study treatment, such as a temporal relationship of the event to study treatment administration, or when other drugs, therapeutic interventions, or underlying conditions do not provide a sufficient explanation for the observed event.
- **Not suspected:** A relationship between the AE and the study treatment can reasonably be ruled out based on lack of any temporal relationship of the event to study treatment administration, or when the subject's underlying condition, medical history, or other therapy provide sufficient explanation for the observed event.

8.4 Follow-up for Adverse Events Definitions

Throughout the study to the final study contact, all AEs will be followed until they resolve or become chronic (as judged by the investigator).

At the final study visit, new AEs, as well as follow-up information for continuing AEs, will be recorded in the CRF and source document. If an SAE (defined in [Section 8.2](#)) is unresolved at the final study visit, it will be followed by the investigator until it resolves or becomes chronic (as judged by the investigator). Follow-up data for such SAEs will be recorded in the source document and reported to the safety monitors (refer to [Section 8.7](#)). Non-serious ongoing AEs will be followed beyond the final study visit at the discretion of the investigator and recorded in the source documents.

8.5 Pregnancy Follow-up

If a subject becomes pregnant during the study, the investigator must inform the Sponsor and collect follow-up data regarding the pregnancy, birth, and status of the child. The Sponsor will provide special CRFs for data collection in the case of pregnancy. Follow-up should be

continued until study close-out at the study center. After close-out, the Sponsor's Safety designee will continue to obtain follow-up information.

Pregnancy should be recorded as a protocol deviation. Pregnancy is not an AE; however, any complication related to pregnancy would be considered an AE.

8.6 Reporting of Technical Complaints

8.6.1 Definitions

A quality complaint is one that is received in writing, electronically, or orally that involves the use or attempted use of a N-PPDS, p-PPDS that identified any defects in the physical properties of the drug product (color, precipitates, viscosity, etc.) or its packaging. Technical complaints also include any identified customer dissatisfaction with the physical characteristic(s) of the study product (dispensing characteristics, labeling, packaging, etc.).

8.6.2 Reporting of Technical Complaints

Any technical complaint should be reported by fax to the Sponsor's Chief Scientific Officer (contact information below) within 24 hours. The complaint report should include the following information:

- Name of the study product
- Strength of study product
- Batch/lot number of study product
- Investigator name, study center name, and contact number
- Date the complaint occurred
- Brief description of the complaint
- Study subject or other individual involved (yes/no):
 - If yes and a study subject, the investigator should report whether any AEs were associated with the complaint (yes/no; if a subject AE was associated with the complaint, refer to [Section 8](#) and attach the AE CRF page to the complaint)
 - If yes and another individual, the investigator should describe the situation and any ill effects on the health of the individual
 - If no, in the investigator's judgment, the investigator should report whether the complaint could reasonably cause an SAE if it recurred under circumstances that did involve a study subject or other person (yes/no)
- Identity of any other investigational or commercial devices involved

The study product and associated packaging that initiated the complaint should be returned to the Chief Scientific Officer (address below) for analysis.

Mati Therapeutics Inc.
Attn: Chief Scientific Officer
[name]
[name]
Burnaby, BC
[name]

[contact]
[contact]

Any complaint about a study product must be reported regardless of whether the defect or deficiency had any effect on a subject or on study personnel.

8.6.3 Punctal Plug Serious Adverse Events and Technical Complaints

The Sponsor will evaluate all SAE reports and technical complaints received in the study to determine if the report meets the definition of an unanticipated ADE. Unanticipated ADEs are defined as follows:

- any serious adverse effect on the health or safety or any life-threatening problem or death caused by, or associated with, a device, if that effect, problem, or death was not previously identified in nature, severity, or degree of incidence in the investigational plan or application or any other unanticipated serious problem associated with a device that relates to the rights, safety, or welfare of subjects.

If the Sponsor determines that any SAE or technical report is an unanticipated ADE, an investigation will be begun immediately. The Sponsor will inform the investigator of any additional reporting requirements beyond those stated in [Section 8.7](#), as applicable.

If the Sponsor determines that an unanticipated ADE presents an unreasonable risk to subjects, the Sponsor will terminate the study as soon as possible. Termination will occur not later than five working days after the Sponsor makes this determination and not later than 15 working days after the Sponsor first received notice of the effect. The Sponsor will report the results of any investigations to the FDA and to investigators, who will also submit the reports to their IRBs, within 10 working days after the Sponsor first received notice of the effect.

8.6.4 Anticipated Adverse Events

The following is a list including, but not limited to, ocular adverse events that are anticipated. Any event that is unlikely but anticipated must have an adverse event form completed and reported to Mati Therapeutics Inc. (see [Section 8.7](#) for reporting details).

- Endophthalmitis/Intraocular infection
- Hypopyon
- IOL dislocation

- Cystoid macular edema
- Pupillary block
- Retinal detachment/tear
- Corneal edema
- Iritis
- Raised IOP requiring treatment
- Visual symptoms requiring lens removal
- Tilt and decentration requiring repositioning
- Residual refractive error resulting in a secondary intervention

NOTE: Wound burps during the first week postoperatively and suture removal are not considered adverse events for this study.

8.7 Reporting Procedures

Adverse events that occur from Visit 2 (1-2 days pre-op) through completion of the end-of-study visit must be documented. The Investigator will assess the AE severity and relationship of the AE to the study drug/device. The Investigator will follow the progress of the study subject until the AE either resolves or becomes medically stable. Treatments and medications required to treat AEs must be recorded.

All adverse events, regardless of severity and whether or not attributed to the drug or drug delivery device, are to be reported to Mati Therapeutics Inc. Adverse events are also to be reported to the site IRB per the IRB's reporting requirements.

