5.5.1.1 Reason for Termination

A study subject will be terminated from the study if in the Investigators medical judgment, it was in the best interest of the study subject that developed or reported: a) moderate to severe signs or symptoms of ocular inflammation or pain, b) reported a serious AEs, regardless of relation to the study drug/device or has died.

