7.7 Prohibited Medications, Treatments and Procedures

7.7.1 Prohibited Medications

The use of any systemic, topical and/or ophthalmic NSAID or corticosteroid within 48 hours of Visit 2 or during the course of the study (Visit 2 to Visit 7) is not allowed unless medically necessary. If an NSAID, corticosteroid or an immunosuppressant is required for any condition (ocular or systemic), the study subject will be terminated from the study, have their masked punctal plug removed and will be followed through Visit 7 (Day 14) or if required until the condition has resolved or has become medically stable.

Investigational/experimental/off-label usages of drugs or devices are not permitted during the study, except as described in the protocol.

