10.4.4 Safety Analyses

All study subjects who are exposed or deemed exposed to study medication will be evaluable for safety analysis. A subject is deemed exposed to study medication if they discontinue the study prior to surgery visit and were implanted with a masked PPDS.

The safety endpoints in this study are adverse events, visual acuity, slit-lamp parameters (Lid, conjunctiva, cornea), fundus findings, and use of rescue medication. Safety variables will be summarized using descriptive statistics.

The type, severity, duration and frequency of reported adverse events will be tabulated for each treatment group, by visit. Adverse events will also be summarized for events and a comparison of the proportion of study patients reporting adverse events between groups will be made using a chi-square test. Additionally, any adverse event experienced by a subject after signing informed consent and before exposure will be presented separately in the safety analysis.

Adverse events will be coded using the Medical Dictionary for Regulatory Activities (MedDRA). Treatment emergent AEs (those occurring after insertion of a study PPDS) will be summarized descriptively: The number and percentage of study subjects who experienced an AE and the total number of AEs will be summarized by system organ class and preferred term. Associated AEs, defined as AEs suspected to be treatment related by the investigator, SAEs and serious associated AEs will also be summarized, if necessary. Summaries of each type of event will be prepared by severity and for all severities combined.

Concomitant medication recorded and used during the study will be coded using the World Health Organization Drug Dictionary and listed by subject. Ocular concomitant medications will be identified by each eye in the listing.

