5.2 Delayed Healing

Topical nonsteroidal anti-inflammatory drugs (NSAIDs) including NEVANAC®, may slow or delay healing. Topical corticosteroids are also known to slow or delay healing. Concomitant use of topical NSAIDs and topical steroids may increase the potential for healing problems.

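### Adverse events are compared as crude proportions with no account of time on the plug, and the plan does not settle when recording ends after an early exit

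*Combined protocol and SAP*

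**What the plan says.** **Recording window.** Section 8.7: "Adverse events that occur from Visit 2 (1-2 days pre-op) through completion of the end-of-study visit must be documented". The window is tied to the end-of-study visit, not to Day 14 and not to plug removal.

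**Analysis.** Section 10.4.4 plans one between-arm safety test: "a comparison of the proportion of study patients reporting adverse events between groups will be made using a chi-square test". The rest is descriptive: "The type, severity, duration and frequency of reported adverse events will be tabulated for each treatment group, by visit", and "Treatment emergent AEs (those occurring after insertion of a study PPDS) will be summarized descriptively". That definition has a start (insertion) but no end. No time at risk, no at-risk denominator by visit, and no split at plug removal or corticosteroid start is specified.

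**Exit linked to efficacy.** Section 5.5.1.1 allows termination, on the Investigator's judgment, for "moderate to severe signs or symptoms of ocular inflammation or pain". Section 7.9.1 uses cell grade, flare grade or moderate to severe pain as rescue criteria for a topical corticosteroid. Under Section 7.7.1 a subject who needs an NSAID, corticosteroid or immunosuppressant is terminated, to "have their masked punctal plug removed and will be followed through Visit 7 (Day 14"), or longer if the condition requires. Section 5.5.1 removes the plug at the last visit, whenever that falls.

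**The concern.** A crude proportion is a fair comparison of harm when both arms are exposed and observed for the same time. Here the events that shorten plug exposure are the ones nepafenac is meant to prevent. If the drug works, more placebo subjects may lose the plug early, and the AE comparison then depends partly on efficacy.

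Two mechanisms are possible.

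- If recording stops at exit, early leavers have less time in which to report an AE.
- If recording continues to Day 14, observation time is equal, but AEs that arise off the plug and on a corticosteroid are attributed to the randomised plug. The appended labels give a reason to care: "Topical corticosteroids are also known to slow or delay healing".

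Safety stands beside efficacy in the study objective (Section 3), and this is the only formal between-arm safety comparison.

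**Working it through.** **1. Figures in the plan.** None can be reproduced for this point. Section 10.5 reports no formal sample size estimation, and the documents give no AE rate or exit rate. The allocation is consistent: 25 blocks × 3 = 75 = 50 + 25.

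**2. When does AE recording end after exit?**

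| Section | Subjects | What it provides | What it leaves open |
|---|---|---|---|
| 5.5 | Terminated | Follow-up through Day 14, or until the condition resolves or is stable | Whether new AEs are sought, or only the exit condition is followed |
| 5.5.2.1 | Terminated | End-of-study safety evaluation with plug removal; counted as having completed | Whether this visit closes the 8.7 window |
| 5.5.2.2 | Discontinued | End-of-study evaluation with plug removal; replaced | No Day 14 follow-up is stated |
| 7.7.1 | Needing an NSAID, corticosteroid or immunosuppressant | Terminated, plug removed, followed through Visit 7 or longer | Section 5.5.1.2 lists use of prohibited therapy under discontinuation instead |
| 7.9.1 | Rescued | Followed through Visit 7, or until resolved or stable | Exit and plug removal are not mentioned, unlike 7.7.1 |
| 8.7 | All | AEs to the end-of-study visit | Which visit that is for an early leaver |

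These sections cannot all be applied as written.

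**3. What an efficacy-linked exit could do to the comparison.**

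Inputs:
- From the documents: n = 50 and 25; full observation T = 15.5 days (insertion 1 to 2 days pre-op, midpoint 1.5, plus 14).
- Assumed: AE risk F over full observation, equal in both arms, with constant hazard λ = −ln(1 − F)/T; exit fractions e_A (N-PPDS) and e_P (placebo); exit on post-op day d, so t = d + 1.5.

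Let q be the probability that an early leaver has a recorded AE.

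- Crude proportion in an arm = (1 − e)F + e·q
- N-PPDS minus placebo = (e_P − e_A)(F − q)

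With more exits on placebo, the sign depends only on whether q is below or above F.

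*Recording stops at exit, and exit is unrelated to AEs.* Then q = 1 − exp(−λt). Central case: F = 40%, e_A = 10%, e_P = 40%, d = 3.
- λ = 0.5108/15.5 = 0.03296; q = 1 − exp(−0.03296 × 4.5) = 0.138
- N-PPDS: 0.9 × 0.40 + 0.1 × 0.138 = 37.4%
- Placebo: 0.6 × 0.40 + 0.4 × 0.138 = 29.5%
- Spurious difference: 0.30 × (0.400 − 0.138) = 7.9 points against N-PPDS
- Mean days observed: 0.9 × 15.5 + 0.1 × 4.5 = 14.4 v 0.6 × 15.5 + 0.4 × 4.5 = 11.1 (ratio 0.77)
- Exact rejection probability of the uncorrected chi-square at two-sided 5%: 9.9%, against 5.5% with equal proportions

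Range over exits of 5%/20% to 15%/60%, exit day 1 to 7 and F of 20% to 60%: difference 1.3 to 20.8 points, time ratio 0.93 to 0.57, rejection 5.1% to 43.2%.

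*The exit event is itself recorded as an AE.* Then q = 1. Central case: 0.9 × 0.40 + 0.1 = 46% v 0.6 × 0.40 + 0.4 = 64%, which is 18 points against placebo. With F = 30% and exits of 10%/50%, it is 37% v 65%.

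*Recording continues to Day 14.* Observation time is equal. If exit entails plug removal, time on the plug still differs by the same ratios (0.57 to 0.93). Any AEs added by the corticosteroid raise q above F and count against placebo.

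**4. Would a rate per subject-day solve it?** Not alone. Take the central case, but with half the cumulative hazard falling before the exit time.
- Risk before exit: 1 − exp(−0.2554) = 0.2254
- Expected days to first AE, before exit time: 0.2254/(0.2554/4.5) = 3.97
- Expected days after exit time, for those who stay: 0.7746 × 0.2254/(0.2554/11) = 7.52
- N-PPDS: (0.36 + 0.0225)/(3.97 + 0.9 × 7.52) = 0.0356 per day
- Placebo: (0.24 + 0.0902)/(3.97 + 0.6 × 7.52) = 0.0389 per day

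The rate ratio is 0.92 although the hazards are equal.

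**The case against.** A reader might infer that AEs are collected only up to each subject's exit, so that an effective plug must look less safe than placebo. The documents do not support that. Sections 5.5, 7.7.1 and 7.9.1 direct follow-up to Day 14, or to resolution or stability, for the very subjects who fail on pain or inflammation or need a corticosteroid. The defect is an unsettled cut-off, not a clearly early one.

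The direction is also open. Section 8.6.4 lists iritis among anticipated events that need an AE form, and the labels list ocular pain as an adverse reaction, so an exit event may itself be an AE. Section 8.2.1, which limits AEs to unanticipated signs and symptoms, leaves this unclear. A proportion counts each subject once, so a subject whose exit event is an AE loses nothing by leaving.

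Unequal exit is plausible but not quantified. The pain-free rates in Section 2.1 (86% and 84% on nepafenac drops v 46% and 38% on vehicle) concern absence of pain, not termination. Most discontinuation reasons in Section 5.5.1.2 are unrelated to efficacy.

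The stakes are modest. This is a 75-subject pilot whose safety analysis is otherwise descriptive, and no decision rule rests on this test. The central 7.9 points is less than one standard error: √(0.374 × 0.626/50 + 0.295 × 0.705/25) = 11.4 points.

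All of this stands. It does not supply the missing cut-off, the missing end to treatment emergence, or a way to tell events on the plug from events after removal. The by-visit table helps little without at-risk denominators.

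**Conclusion.** The point holds as a gap in definition and presentation. Section 10.4.4 compares crude AE proportions without time at risk and attributes all AEs after insertion to the randomised plug, while plug removal and corticosteroid use can depend on efficacy. Whether observation time also differs cannot be settled from the text.

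The documents fix neither size nor sign. The 1.3 to 20.8 points against N-PPDS applies only if recording stops at exit, exits are more frequent on placebo at the assumed rates, hazards are constant and equal, and exit is unrelated to AEs. Recording exit events as AEs reverses the sign; corticosteroid-related AEs push the same way. A chi-square result in either direction could not be read as evidence about the plug alone. The primary endpoint is unaffected.

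**What to change.** 1. Reconcile Sections 5.5, 5.5.2.1, 5.5.2.2, 7.7.1, 7.9.1 and 8.7 so that a single AE recording cut-off applies to every subject with an inserted plug, and say whether new AEs are sought after exit. The text should also be made consistent on whether corticosteroid use ends participation; which rule applies is for the sponsor to decide.
2. In Section 10.4.4, report days on plug and days of AE observation by arm. Tabulate in separate columns the AEs that start before, and those that start after, plug removal or loss or the start of a rescue corticosteroid.
3. Keep the crude counts and proportions and label the chi-square descriptive. Add exposure-adjusted rates or cumulative incidence as supplementary, stating that the first assumes a constant hazard and that censoring at plug removal is informative.

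Plug, visit and medication dates are already required in source documents (Section 11.1), so item 2 needs no new data. Item 1 must be settled before data collection ends, because no analysis recovers AEs that were never recorded. The cost is a short clarification, one more table and a less simple headline figure.
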